2. To determine the feasibility and tolerability of LT as an intervention strategy to reduce fatigue in pMS by reporting the adherence data with the study intervention and participant-reported side effects.

Hypothesis 2: LT will be both feasible and well-tolerated in pMS.

III. SUBJECT SELECTION:

A. Inclusion/Exclusion Criteria:

a. *Inclusion Criteria:* (1) relapsing remitting or secondary

progressive MS based on McDonald Criteria (2010)¹⁵ (2) ≥ 18 and ≤ 70 years old, (3) presence of fatigue defined as FSS ≥ 36 on screening (range 7-63 possible points).¹⁶

- b. *Exclusion criteria:* (1) change in an anti-depressant, (2) fatigue medication regimen, or MS disease modifying therapy up to 4 weeks prior to study screening, (3) Beck Depression Inventory II score >20 , (4) shift work, (5) use of photosensitizing medication, (6) presence of eye trauma or acute optic neuritis within the preceding 3 months or presence of macular degeneration or other retinal disease, (7) history of traumatic brain injury or (8) probable (untreated) sleep apnea based on Berlin questionnaire (9) significant anemia (10) history of mania, (11) MS relapse in the preceding four weeks, (12) current pregnancy, (13) known photosensitivity (14) other complicating illness preventing study completion. Patients will be withdrawn from study participation if they experience a clinical relapse requiring hospitalization or treatment with steroids during the study period. They will also be withdrawn if there is a change in disease modifying therapy for MS, depression or fatigue during the study period.

B. Subject Recruitment:

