Participants will be recruited from the MS Clinic at Massachusetts General Hospital (MGH). 700 pMS are followed in this clinic. In preliminary screening, $\sim 2/3$ of MS patients at MGH have a FSS ≥ 36 (mean 45.9, standard deviation 15.2 points) and will be eligible for participation. We will use flyers placed throughout the hospital as well as letters to eligible patients in order to assist with recruitment. We will use MGH's Research Subject Volunteer Program (RSVP), a participant matching service, to identify subjects with enthusiasm for the project. If the participant is a patient of the principal investigator, a research physician or study coordinator will explain the study so they do not feel obligated to participate. Subjects between 18-70 years old will be recruited for they study. For older subjects, best clinical judgment will be used to determine if participation is feasible.

IV. SUBJECT ENROLLMENT:

- A. **Methods of enrollment, procedures for obtaining informed consent, and randomization:** Following a redcap screening survey (Beck Depression Inventory, Fatigue Severity Scale, Berlin Questionnaire, Inclusion/exclusion criteria) and a baseline visit, eligible participants will be consented and randomized using a computer-based randomization generator 1:1 to (a) white LT (10,000 lux), or (b) dim red LT (<300 lux). Dim red LT is a widely accepted controlled condition in clinical studies of LT. In attempt to reduce placebo effect, the participants will be informed that this study will examine the effect of two different light spectra on fatigue and that one will be placebo. They will be informed that they will not know the

group they are in. Informed written consent will be obtained at the time of enrollment at the screening/baseline visit.

V. STUDY PROCEDURES:

A. Study visits and parameters to be measured, data to be collected and when the data is to be collected:

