Interested patients will be identified through the MS clinic at MGH, the RSVP, the Partners Clinical Trials website or alerted by flyer/letter. Following a phone call to explain the details and requirements of the study, interested participants will undergo a screening survey administered through redcap, link sent by email. This survey will include questions regarding the inclusion/exclusion criteria, the Fatigue Severity Scale (≥ 36), the Beck Depression Inventory (≤ 20), and the Berlin Questionnaire to screen the participant for eligibility. Participants who are eligible and remain willing to participate will then be scheduled for an in-person visit with either the principal investigator (PI) or another physician involved in the study for a baseline visit. The following assessments will be administered by the study PI/research physician at the baseline visit: (1) the Kurtzke Extended Disability Status Scale (EDSS), (2) FSS, (3) Pittsburg Sleep Quality Index (PSQI), (4) Epworth Sleepiness Scale (ESS), (5) Multiple Sclerosis Quality of Life-54 (MSQOL-54). Additionally data will be obtained from patient report and chart review on the patient's history of RRMS or SPMS including time from diagnosis, disease modifying therapy, baseline neurologic symptoms, imaging features such as presence or absence of spinal cord lesions as well as data on medical comorbidities and medications used. Data on the use of caffeine, alcohol and tobacco will also be collected. The participants most recent Vitamin D level will also be obtained from their medical record. This will be collected in order to assess whether response to light therapy differs amongst patients with differing levels of vitamin D deficiency. Studies in patients with MS fatigue show mixed results regarding the relationship of fatigue with vitamin D level and supplementation ¹⁹⁻²¹.

At the baseline visit, participants will be randomized to BWL or DRL. The research coordinator will be aware of the assignment and will distribute the appropriate light therapy boxes during the visit. The PI and research physician will be blinded to treatment assignment so as not to bias follow-up visit assessments. The group assignments will be kept in an excel file that only the research coordinator has access to to maintain blindedness.

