The lights are tested by the supply company before distribution to ensure they meet advertised levels of lux output. Lights are turned on by the study team to make sure they work before being provided to study participants. In cases where bulbs burn out, they are replaced with new bulbs purchased from the same supply company.

VI. BIostatistical Analysis:
Specific data variables, study endpoints, statistical methods, power analysis

The primary outcome measure will be change in the average FSS after

the 4-week study period in the bright light “active” versus the dim light “control” groups. There are no available data on FSS in response to bright LT in pMS. To test the specific aim of change of ≥ 15 points, we used the conventional values of $\alpha=0.05$ and $\beta=0.80$ for 2-tailed tests of probability with equally sized groups. For a difference in ≥ 15 points, with an estimated standard deviation of 15.2 points and mean of 45.9 points from preliminary data collection at the MGH MS Clinic, we require a minimum of 15 people in either group. The primary aim will compare the mean change in FSS scores before initiation and after completion of LT, in an intention to treat analysis comparing the active and control condition groups. The secondary outcome measure will be a change in the global VAFS scores after light therapy in both groups. Frequencies will be used to describe baseline characteristics across treatment arms. χ^2 statistics or Fisher’s exact test will be used to compare the differences between groups. VAFS will be evaluated using a mixed-effects model which accounts for correlation between repeated measurements. Participant logbooks will be used to generate summary statistics and to graphically display fatigue patterns throughout the day among pMS in both groups. Logbooks will also be used to qualitatively assess the safety and tolerability of LT.

RISKS AND DISCOMFORTS:

Device complications/malfunctions and Psychosocial (non-medical risks)

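### Efficiency only: the primary FSS comparison names no covariate, and prespecifying adjustment for the baseline FSS already collected could narrow the interval, at an expected loss of at most about 4% of variance

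*Combined protocol and SAP*

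**What the plan says.** Section VI states the primary analysis as follows: "The primary aim will compare the mean change in FSS scores before initiation and after completion of LT", by intention to treat, active against control. It gives no test, model or covariate for FSS. For the secondary outcome it does name a model: "VAFS will be evaluated using a mixed-effects model which accounts for correlation between repeated measurements".

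The covariate is already in hand. Section V.A lists the assessments made "at the baseline visit: (1) the Kurtzke Extended Disability Status Scale (EDSS), (2) FSS", and FSS is repeated at the end-of-treatment visit. Section IV.A describes allocation thus: "eligible participants will be consented and randomized using a computer-based randomization generator 1:1". No stratification is mentioned.

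Two further statements affect the size of any gain. Section III.A requires "presence of fatigue defined as FSS ≥ 36 on screening (range 7-63 possible points". Section III.B says that about two-thirds of clinic patients "have a FSS ≥ 36 (mean 45.9, standard deviation 15.2 points) and will be eligible for participation".

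**The concern.** Comparing mean change subtracts the whole baseline score, which amounts to assuming that end-of-treatment FSS rises one point for each point of baseline FSS. When the true slope is below 1, subtraction over-corrects and adds the noise of the baseline score to the outcome. A model with baseline FSS as covariate estimates the slope instead. Both approaches are unbiased over randomisations; they differ in variance.

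With a planned minimum of 15 per group the interval will be wide, and Section VII says that the results are to inform a larger randomised study. Naming the model in advance also settles a choice now left open: since none is named for FSS, either an adjusted or an unadjusted analysis could later be presented as the planned one.

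**Working it through.** **Inputs from the documents.** 15 per group (N = 30), two-sided alpha 0.05, a 15-point difference and SD 15.2 (Section VI); mean 45.9 (Sections III.B and VI); entry at FSS 36 or more and score range 7 to 63 (Section III.A).

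**Inputs that must be assumed.** r, the correlation of baseline with end-of-treatment FSS, and q, the correlation of screening with baseline FSS. Neither is given.

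**The plan's own figure.** The normal-approximation formula gives 2 × (15.2 × (1.960 + 0.842) / 15)² = 16.1, so 17 per group against the stated 15. At 15 per group, power is 77.1% by the normal approximation and 74.2% by the t test. The starting point is therefore slightly below 80%; that gap is not pursued here.

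**Bound on the loss.** Let c be the correlation of baseline FSS with FSS change. Under a linear normal model, adjusted/unadjusted variance = (1 − c²) × (N − 3)/(N − 4). This is largest at c = 0, that is, when the true slope is 1: 27/26 = 1.038. Residual degrees of freedom fall from 28 to 27, so interval width grows by √(27/26) × 2.0518/2.0484 = 1.021, about 2%. The bound holds whatever the two SDs are.

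**Equal SDs, no range restriction.** The ratio becomes (1 + r)/2 × 27/26:

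| r | ratio |
|---|---|
| 0 | 0.519 |
| 0.3 | 0.675 |
| 0.5 | 0.779 |
| 0.7 | 0.883 |
| 0.8 | 0.935 |
| 0.9 | 0.987 |

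Break-even is r = 2 × 26/27 − 1 = 0.926. Using 15.2 as the SD of change, which fits equal SDs of 15.2 only at r = 0.5 because SD(change) = SD × √(2(1 − r)), t-test power at r = 0.5 goes from 74.2% to 83.9% for 15 points.

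**Why these figures are too favourable.** Scores confined to 36–63 cannot have a population SD above 27/2 = 13.5. So 15.2 must describe the whole clinic, not those who qualify. Selecting on screening FSS shrinks the baseline SD relative to the follow-up SD, which moves the slope towards 1. With a baseline/follow-up SD ratio k, the variance ratio is (1 − r²)/(1 + k² − 2kr) × 27/26. At k = 0.8 and r = 0.3, 0.5, 0.7 and 0.9, variance changes by −18.5%, −7.3%, +1.8% and −1.3%.

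**With entry at 36 or more.** Simulation: 40,000 trials per setting, 15 per group; screening, baseline and follow-up drawn with mean 45.9 and SD 15.2; only screening scores of 36 or more kept; any treatment effect applied before baseline and follow-up scores are limited to 7–63. The screening-to-follow-up correlation is set to r or to q × r. Variance ratios:

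| r | screening-to-follow-up | q = 0.9: null / 15 points | q = 0.99: null / 15 points |
|---|---|---|---|
| 0.3 | r | 0.80 / 0.82 | 0.83 / 0.87 |
| 0.5 | r | 0.86 / 0.89 | 0.90 / 0.94 |
| 0.5 | q × r | 0.88 / 0.91 | 0.91 / 0.93 |
| 0.7 | r | 0.90 / 0.96 | 0.96 / 0.99 |
| 0.8 | r | 0.93 / 0.98 | 0.98 / 1.02 |
| 0.8 | q × r | 0.97 / 1.02 | 0.99 / 1.03 |

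Monte Carlo error is about 0.01 per ratio. At r = 0.5 (screening-to-follow-up set to r), power for 15 points goes from 78.7% to 82.9% (q = 0.9) or from 80.6% to 82.7% (q = 0.99). At r = 0.9 and q = 0.99 there is a small loss: 1.01 with no effect, 1.04 with 15 points. The largest power loss found was 0.8 percentage points (79.0% to 78.2%, for a 10-point effect). Type I error was 4.7% to 5.3% for both methods.

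**The case against.** The strongest reply is that nothing here is wrong. The planned comparison is valid, covariates are not excluded, the gain cannot be computed from the documents, and adjustment can lose slightly. All of that stands, and it limits the point to an efficiency improvement.

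The size can fairly be challenged too. The simulation is not calibrated to the clinic data: taking 45.9 and 15.2 as values before scores are limited to 7–63 gives a clinic population with mean 44.9, SD 13.4 and 74% at 36 or more, against the reported 45.9, 15.2 and about two-thirds. The ratios are therefore indicative. Lower values of q give larger gains (0.73 at r = 0.5 and q = 0.5 with no effect), but that setting has screening FSS correlating no better with the baseline visit than with a score taken at least six weeks after it. It should not carry the argument.

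A reader might infer three stronger things.

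- *That the unadjusted comparison is biased or inflates type I error.* Randomisation protects it, and the simulated error rates agree.
- *That a one-third saving in variance is expected, or is the most possible.* It comes from choosing r = 0.3 with equal SDs and no selection. It is neither a forecast nor a limit: r = 0 would give −48%.
- *That baseline FSS may be taken after assignment, because Section V.A says* "At the baseline visit, participants will be randomized to BWL or DRL" *and that the coordinator* "will distribute the appropriate light therapy boxes during the visit". Section IV.A puts randomisation after the screening survey and a baseline visit, and Section V.A describes the assessments before it describes randomisation. The planned change score needs that order just as much, so it is no obstacle particular to adjustment.

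**Conclusion.** The point holds as an efficiency improvement. Section VI leaves baseline FSS to act only through subtraction when it could be a covariate. The one firm figure is the ceiling on expected loss, about 4% of variance or 2% of interval width at 15 per group, under a linear normal model. The gain depends on correlations that the documents do not supply. Within the range-restricted settings considered (q 0.9–0.99, r 0.3–0.8), it runs from about a fifth of the variance to nothing or a loss of up to 3%. The larger closed-form savings of 22% at r = 0.5 and 32.5% at r = 0.3 ignore the entry criterion and rest on assumption. The case for adjusting is the asymmetry: a small, capped downside against a moderate possible gain from data already collected.

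**What to change.** In Section VI, name the primary model. Suggested wording:

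> The primary analysis is a linear regression of end-of-treatment FSS on randomised arm with baseline-visit FSS as covariate, participants analysed as randomised, two-sided alpha 0.05, reporting the adjusted mean difference with 95% CI.

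Using FSS change as the response in the same model gives the identical arm effect. Keep raw mean change by arm as a descriptive summary.

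The cost is one sentence and one degree of freedom. No new measurement, visit or participant is needed, and the randomisation and assessment schedule stay as they are.

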After randomization the subjects will begin the study period. The study period will include a 2-week baseline period without any light therapy treatment, a four week treatment period and a four week follow-up (wash-out) period. Throughout the study period, participants will record their fatigue using the Visual Analogue Fatigue Scale (VAFS) four times daily, starting after waking up, and

every four hours thereafter (at least 3x per day). The VAFS is a simple, validated 10-point scale ranging from 1 to 10 in which participants can report their fatigue as a snapshot at that particular moment.¹⁸ Data collection will occur by participants in self-report fashion on paper that will be returned to the study staff at the end of the study period. During the entirety of the study period including baseline and wash-out, patients will also collect a sleep diary which requires filling out once per day (<1 minute). During the four week treatment period patients will record their use of light therapy in a log as well as any side effects they are experiencing. Patients will be instructed to sit in front of the light box with eyes approximately 18.5 inches from the light source. They will use the box for one hour twice per day, in the morning starting two hours after awakening and in the evening starting 3 hours before bedtime. Eyes should be open while using LT but patients do not have to look directly at the light and can eat, read, watch television etc. during use.

There will be two visits with the principal investigator (PI) including the baseline visit described above, a visit with the PI at the end of the treatment period in which participants will perform a FSS, MSQOL-54 and discuss their experiences with LT. Final follow up surveys (FSS and MSQOL54) will be sent using redcap by email following the 4-week washout period. Patients will be reminded not to reveal their treatment assignment to the examining blinded physician.

- B. Device to be used:** The light box used for LT (SunRay by *The Sunbox Company*, Gaithersburg, Maryland, USA) is approximately 15.5" tall x 23" wide x 3.25" deep and is designed to stand on a desk or tabletop. It can be used both in the home or office. The light is delivered at a downward angle to maximize the effectiveness. The box runs on 124 watts and contains full spectrum 5000k 10,000 lux bulbs. Bright light treatment requires at least 2,500 lux to be effective.¹⁷

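### Tolerability under Aim 2 is to be assessed qualitatively, with no planned by-arm counts, confidence intervals, between-arm difference or criterion, although both randomised arms keep the same log

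*Combined protocol and SAP*

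**What the plan says.** Section II (Specific Aims) has two numbered aims. The second carries its own hypothesis: "Hypothesis 2: LT will be both feasible and well-tolerated in pMS". The aim is to be met "by reporting the adherence data with the study intervention and participant-reported side effects".

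Section V.A describes the data. During the four-week treatment period "patients will record their use of light therapy in a log as well as any side effects they are experiencing". The instruction is not limited to one arm.

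Section VI has four sentences that could bear on the analysis of these data:

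- On safety and tolerability directly: "Logbooks will also be used to qualitatively assess the safety and tolerability of LT".
- On logbooks more generally: "Participant logbooks will be used to generate summary statistics and to graphically display fatigue patterns throughout the day among pMS in both groups".
- On frequencies: "Frequencies will be used to describe baseline characteristics across treatment arms".
- Immediately after that, on chi-square or Fisher tests: "exact test will be used to compare the differences between groups".

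Sections VIII.A to VIII.D add a coordinator call two weeks into treatment, review of efficacy, tolerability and feasibility at treatment visits, and physician review of the treatment and side-effect logs. These are monitoring activities. They give no analysis rule.

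**The concern.** One of the trial's two specific aims has a stated hypothesis, but its analysis stops at a qualitative reading for tolerability and an unspecified report for adherence. Two things are lost.

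First, people with MS may record complaints during four weeks whatever light they sit in front of. The randomised dim red arm is the design's means of showing how many. If side effects are not tabulated by arm, that information goes unused.

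Second, a statement about tolerability from roughly 15 people per arm is imprecise, and a narrative summary does not show how imprecise. Section VII says the data should inform a larger randomised study. Planning that study needs adherence and side-effect rates with their uncertainty.

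**Working it through.** **1. The plan's own figure.** The only sample size is a minimum of 15 per group, derived for the FSS comparison in Aim 1. The inputs in section VI are a difference of 15 points, SD 15.2, two-sided alpha 0.05 and 0.80 (written as beta, read as power). The normal-approximation formula gives n per group = 2 × [15.2 × (1.960 + 0.842) / 15]² = 16.1, rounded up to 17. That is close to the stated 15. No rate, margin or threshold is stated for Aim 2, so there is nothing to reproduce there. I take 15 per arm as the working size.

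**2. What section VI covers for Aim 2.**

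| Sentence in section VI | Content it names | Adherence or side effects named? |
|---|---|---|
| Frequencies | Baseline characteristics | No |
| Chi-square or Fisher | Differences between groups, directly after baseline | No |
| Logbook summary statistics and graphs | Fatigue patterns, both groups | No |
| Logbooks, qualitative | Safety and tolerability | Yes, qualitatively |

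None gives a by-arm count, an interval, a difference or a criterion for Aim 2.

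**3. Scheduled sessions.** Two sessions a day for four weeks: 2 × 28 = 56 per participant.

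**4. Precision at 15 per arm.** The documents give no side-effect or adherence rates, so every count below is an assumption. The exact (Clopper-Pearson) 95% limits for x of n are: lower = 2.5th percentile of Beta(x, n − x + 1); upper = 97.5th percentile of Beta(x + 1, n − x). For x = 0 the upper limit reduces to 1 − 0.025^(1/n).

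- 0/15 with a given side effect: upper limit 1 − 0.025^(1/15) = 21.8%.
- 3/15 (20%): 4.3% to 48.1%.
- 12/15 adherent (80%): 51.9% to 95.7%.

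For a difference, take 5/15 on bright light against 2/15 on dim red. This is 33.3% − 13.3% = 20.0 percentage points, with a Newcombe 95% interval of −10.5 to 46.7.

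**5. Would a significance test help?** Power of the two-sided Fisher test at 0.05 is the sum, over all pairs of counts (a, b) from 0 to 15 with p ≤ 0.05, of the product of the two binomial probabilities.

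| Assumed rates, bright vs dim red | Power at 15 per arm |
|---|---|
| 30% vs 10% | 0.15 |
| 40% vs 20% | 0.11 |
| 40% vs 10% | 0.33 |
| 50% vs 10% | 0.54 |
| 60% vs 10% | 0.74 |

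A non-significant test would say little, so estimation is the better choice.

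**6. Is a criterion feasible at this size?** As an example only, suppose feasibility is declared if at least 13 of 15 participants are adherent. Under binomial sampling this has a 0.027 chance of success when the true rate is 60% and a 0.82 chance when it is 90%. A rule that can fail is therefore workable. The level is for the sponsor to choose.

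**The case against.** The strongest defence is that Aim 2 is descriptive and the plan says so. Section II promises to report adherence and side effects, so some descriptive output is planned. The FSS is the primary outcome and the VAFS the secondary, Aim 2 is not powered, and the trial is meant to inform a larger one. Description is a legitimate choice for such an aim. That stands, and it argues for estimates with intervals over tests. It does not supply the arm breakdown or the intervals.

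A looser reading would bring side effects under the chi-square/Fisher sentence, or adherence under the summary-statistics sentence. The wording does not exclude this. But the first follows directly from baseline characteristics, the second names only fatigue patterns, and the next sentence deals with safety and tolerability separately.

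A reader might infer more than the documents support in three ways:

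- That side effects will not be compared between arms. A comparison is unplanned; it is not ruled out.
- That Hypothesis 2 will be accepted whatever the logs show. No acceptance rule is stated, and very low adherence or many withdrawals, once reported as section II promises, would visibly contradict it.
- That the qualitative reading is the whole of Aim 2. It is the only tolerability method in section VI, but section II adds the reporting of adherence and side effects.

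Finally, with about 15 per arm, even a by-arm comparison will separate background complaints from light effects only when the difference is large. That is correct, and it limits what the fix can deliver.

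**Conclusion.** The point holds as a minor weakness in the choice of analysis. For one of two specific aims, the stated tolerability method is qualitative, and no by-arm count, interval, between-arm difference or criterion is planned, although the data for the first three should largely come from logs kept in both arms.

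The illustrated size is an upper limit of 21.8% when no events are seen, and an interval from about half to nearly all when 80% adhere. These figures assume the counts shown and 15 per arm; recruitment above that minimum would narrow them. They show how little a qualitative summary could establish. They do not show an arithmetical error in the plan. The primary FSS analysis is unaffected.

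**What to change.** In section VI, replace the qualitative logbook assessment with a table by randomised arm giving:

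- adherence per participant, as logged sessions out of the 56 scheduled, where the log records individual sessions (section V.A says only that use is recorded, so the log format should be confirmed);
- number completing treatment;
- number with each side effect;
- number stopping because of a side effect.

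Give exact 95% confidence intervals for the proportions in each arm, and the between-arm difference with its confidence interval. State that this is estimation and not a significance test. Free-text comments can still be summarised alongside.

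Report Hypothesis 2 as an estimate, not as confirmed, unless the sponsor fixes an adherence criterion before any logs are reviewed. Fixing it before unblinding would not be enough, because adherence and tolerability are discussed at the two-week call and the logs are reviewed during follow-up, and the coordinator already knows the allocation.

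The cost is one table from data already being collected. The downside is that wide intervals will limit the tolerability claim, which is appropriate at this sample size.
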